## 9. SAFETY AND TOLERABILITY ANALYSIS

Safety will be evaluated from reported AEs, physical examinations, local tolerability assessments, changes in clinical laboratory values, and changes in vital signs/weight. No inferential statistical tests will be performed.

All safety analyses will be performed on the Safety population.

Presentation of treatments for safety analysis summary tables are described in [Section 6.1.9](#).

### 9.1. Adverse Events

All AEs, TEAEs, and SAEs will be coded using the MedDRA dictionary version 23.0.

A TEAE is defined as an AE within an onset on or after the day of study treatment through study completion. An overall summary of TEAEs will be provided; this will present number and percent of subjects who reported at least 1 of the following: TEAE (including all TEAEs, TEAEs by maximum severity, and related TEAEs), SAE, discontinued the study due to a TEAE, discontinued the study drug due to a TEAE, or a TEAE resulting in death.

The number and percent of subjects reporting TEAEs, grouped by MedDRA system organ class (SOC) and preferred term, will be tabulated by severity or by greatest relationship to study drug and treatment group within cohort. In the case of multiple occurrences of the same TEAE within the same subject, each subject will only be counted once for each preferred term. Additionally, the number and percent of subjects reporting related TEAEs will be summarized by MedDRA SOC, preferred term, severity, and treatment group within cohort.

Relationship to study drug will be mapped as follows: related = likely related, probably related, or possibly related; unrelated = unlikely related or unrelated. In the summaries showing severity and relationship to study medication the event with the maximum severity (mild < moderate < severe < life-threatening < death) or strongest relationship (unrelated < related) will be reported. If a particular event is missing the severity and/or relationship, then the strongest possible severity or relationship will be assumed for analysis (severity = severe, relationship = related).

In the AE data listings, all AEs will be displayed. Any AEs that are treatment emergent will be flagged.

### **9.1.1. Adverse Events Leading to Withdrawal**

A summary of incidence rates (frequencies and percentages) of TEAEs leading to withdrawal of study drug by treatment group within cohort, SOC, and preferred term will be prepared for the Safety population. Additionally, this table will be repeated for related TEAEs leading to withdrawal of study drug and all TEAEs leading to withdrawal from the study. No inferential statistical tests will be performed.

A data listing of AEs leading to withdrawal of study drug will also be provided, displaying details of the event(s) captured on the eCRF.

### **9.1.2. Deaths and Serious Adverse Events**

Any deaths that occur during the study will be listed.

Serious adverse events (SAEs) will be listed and tabulated by SOC and preferred term and presented by treatment group within cohort, by severity, and by relationship to study treatment.

## **9.2. Local Tolerability Assessments**

The investigator's assessment of the application site reaction will be summarized by study visit and treatment group within cohort using both categorical methods (number and percentage of subjects with each score) as well as continuous methods (e.g., mean, median). Categorical summaries will be provided for dermal response as well as other effects. No inferential statistical tests will be performed.

The subject's assessment of the application site reaction will be summarized similarly.

## **9.3. Clinical Laboratory Evaluations**

Laboratory test results will be summarized descriptively by treatment and study visit as both observed values and change from baseline values for continuous hematology, chemistry (including thyroid), and urinalysis results. Categorical urinalysis results will be summarized using frequencies by study visit and treatment group within cohort.

The number of subjects with clinical laboratory values below, within, or above the normal range by study visit and in relation to baseline will be tabulated for each clinical laboratory analyte by treatment group within cohort (shift table).

Abnormal results will be flagged in the listings. In addition, pregnancy test results and hormonal laboratory results will be listed.

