4.10 Treatment Stopping Rules

If a subject has non-cutaneous adverse events of concern, clinically significant laboratory values or any condition that the Investigator determines could possibly be related to the investigational product, the Investigator should immediately contact the Medical Monitor to discuss if the subject should be discontinued from treatment with investigational product.

Treatment for any individual subject will be discontinued if the subject experiences:

- A serious adverse event (SAE) or a clinically significant non-serious AE which in the opinion of the Principal Investigator or Medical Monitor warrants discontinuation from the study for that subject's well-being.
- A treatment-emergent severe (Grade 3 or higher) laboratory abnormality (confirmed by repeat sample).
- A severe infection (Grade 3 or higher)
- An Ischemic or thromboembolic cardiovascular event (regardless of Grade)
- Any other adverse event that represents an unacceptable risk to the subject (e.g., Grade 3 or higher)

As noted above, study treatment must be discontinued immediately in the event of a female subject's pregnancy.

Treatment should be interrupted:

- If a subject develops an application site reaction with the clinical appearance of an 'irritation reaction', and with a severity of a Dermal Response Score of 5 (erythema, edema and papules) or greater on the scale of Berger and Bowman, treatment should be interrupted for up to one week and may then be resumed if the reaction has, in the opinion of the Investigator, adequately resolved.

Treatment should be discontinued:

- If the application site reaction reoccurs, treatment should be discontinued permanently, and the subject followed until the reaction resolves.

For cases of suspected allergic contact dermatitis, the Medical Monitor and Sponsor should be notified and there should be discussion about performing patch testing to further evaluate. Patch testing is encouraged in such cases.

Phase 2b (Cohort 2)

In the event of a medical emergency where unblinding is required to provide medical care to the subject, refer to the most current IRT plan and Breaking Treatment Codes ([Section 4.6.1](#)). Contact the Medical Monitor and the Sponsor promptly.

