5.6 Unscheduled Visit

Unscheduled visits may be necessary to repeat testing following abnormal laboratory results, for follow-up of AEs, or for any other reason, as warranted in the judgement of the Investigator.

The following information will be collected for all subjects:

- Concomitant medications/procedures
- AEs
- BSA, IGA, HESCI

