### 6.1.5. Analysis Visit Windows

#### 6.1.5.1. Non-Diary Assessments

Visits will be analyzed as scheduled (i.e., not subject to visit windowing). Unscheduled, early termination, and/or repeated measurements will only be included if a scheduled measurement is not available and the unscheduled, early termination, or repeated measurement falls within the analysis visit windows as described in Table 3 (Cohort 1 [Phase 1]) and Table 4 (Cohort 2 [Phase 2b]). The windows follow the Schedule of Events in Table 1 and Table 2. Visits falling outside of these windows will not be windowed (e.g., an unscheduled visit before first application of study drug). Unscheduled/repeated measurements will be listed.

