**Table 4: Analysis Visit Windows (Cohort 2 [Phase 2b])**

Visit Name	Analysis Visit Number	Target Start Day	Lower Limit	Upper Limit
Week 2	3	14	2	22
Week 4	5	28	23	42
Week 8	6	56	43	70
Week 12	7	85	71	90
Week 13	8	92	91	--

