### 13.1.3.4. Abnormal Laboratory Values

Table Number	Population	Table Title / Summary
NA		

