### 13.1.3.5. Laboratory Data Summary Tables

Table Number	Population	Table Title / Summary
Table 14.3.5.1.1.1	Safety	Cohort 1: Summary of Serum Chemistry Laboratory Results (Standard Units) by Study Visit
Table 14.3.5.1.1.2	Safety	Cohort 2: Summary of Serum Chemistry Laboratory Results (Standard Units) by Study Visit – Cohort 2
Table 14.3.5.1.2.1	Safety	Cohort 1: Shift from Baseline in Clinical Chemistry Laboratory Results (Standard Units) by Study Visit
Table 14.3.5.1.2.2	Safety	Cohort 2: Shift from Baseline in Clinical Chemistry Laboratory Results (Standard Units) by Study Visit
Table 14.3.5.2.1.1	Safety	Cohort 1: Summary of Hematology Laboratory Results (Standard Units) by Study Visit
Table 14.3.5.2.1.2	Safety	Cohort 2: Summary of Hematology Laboratory Results (Standard Units) by Study Visit
Table 14.3.5.2.2.1	Safety	Cohort 1: Shift from Baseline in Hematology Laboratory Results (Standard Units) by Study Visit
Table 14.3.5.2.2.2	Safety	Cohort 2: Shift from Baseline in Hematology Laboratory Results (Standard Units) by Study Visit
Table 14.3.5.3.1.1	Safety	Cohort 1: Summary of Quantitative Urinalysis Laboratory Results (Standard Units) by Study Visit
Table 14.3.5.3.1.2	Safety	Cohort 2: Summary of Quantitative Urinalysis Laboratory Results (Standard Units) by Study Visit
Table 14.3.5.3.2.1	Safety	Cohort 1: Shift from Baseline in Quantitative and Qualitative Urinalysis Laboratory Results (Standard Units) by Study Visit
Table 14.3.5.3.2.2	Safety	Cohort 2: Shift from Baseline in Quantitative and Qualitative Urinalysis Laboratory Results (Standard Units) by Study Visit
Table 14.3.5.3.3.1	Safety	Cohort 1: Summary of Qualitative Urinalysis Laboratory Results by Study Visit
Table 14.3.5.3.3.2	Safety	Cohort 2: Summary of Qualitative Urinalysis Laboratory Results by Study Visit

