Baseline		
n	XX	
Mean (SD)	XX.X (X.XX)	
Median	XX.X	
Min, Max	XX, XX	
Week 1		
n	XX	XX
Mean (SD)	XX.X (X.XX)	XX.X (X.XX)
Median	XX.X	XX.X
Min, Max	XX, XX	XX, XX
Week 2		
n	XX	XX
Mean (SD)	XX.X (X.XX)	XX.X (X.XX)
Median	XX.X	XX.X
Min, Max	XX, XX	XX, XX
Week 3		
n	XX	XX
Mean (SD)	XX.X (X.XX)	XX.X (X.XX)
Median	XX.X	XX.X
Min, Max	XX, XX	XX, XX

*Continue for other parameters. Sort alphabetically by parameter.*

Abbreviations: QD = once daily; SD = standard deviation.  
 Note: Subjects are summarized by treatment received. Results from the thyroid panel are included.  
 Baseline is the last non-missing measurement taken before the first application of study drug.  
 Change from baseline is calculated as result – baseline result.  
 Reference Listings: 16.2.8.1.1, 16.2.8.1.4

Table 14.3.5.1.1.2  
 Cohort 2: Summary of Clinical Chemistry Laboratory Results (Standard Units) by Study Visit  
 Safety Population

Study Visit Statistic	Cohort 2					
	ARQ-252 Cream 0.3% QD (N=XX)		ARQ-252 Cream 0.3% BID (N=XX)		ARQ-252 Cream 0.1% QD (N=XX)	
	Observed	Change	Observed	Change	Observed	Change
Baseline						
n	XX		XX		XX	
Mean (SD)	XX.X (X.XX)		XX.X (X.XX)		XX.X (X.XX)	
Median	XX.X		XX.X		XX.X	
Min, Max	XX, XX		XX, XX		XX, XX	
Week 4						
n	XX	XX	XX	XX	XX	XX
Mean (SD)	XX.X (X.XX)	XX.X (X.XX)	XX.X (X.XX)	XX.X (X.XX)	XX.X (X.XX)	XX.X (X.XX)
Median	XX.X	XX.X	XX.X	XX.X	XX.X	XX.X
Min, Max	XX, XX	XX, XX	XX, XX	XX, XX	XX, XX	XX, XX
Week 8						
n	XX	XX	XX	XX	XX	XX
Mean (SD)	XX.X (X.XX)	XX.X (X.XX)	XX.X (X.XX)	XX.X (X.XX)	XX.X (X.XX)	XX.X (X.XX)
Median	XX.X	XX.X	XX.X	XX.X	XX.X	XX.X
Min, Max	XX, XX	XX, XX	XX, XX	XX, XX	XX, XX	XX, XX
Week 12						
n	XX	XX	XX	XX	XX	XX
Mean (SD)	XX.X (X.XX)	XX.X (X.XX)	XX.X (X.XX)	XX.X (X.XX)	XX.X (X.XX)	XX.X (X.XX)
Median	XX.X	XX.X	XX.X	XX.X	XX.X	XX.X
Min, Max	XX, XX	XX, XX	XX, XX	XX, XX	XX, XX	XX, XX

**Repeat this page for the remaining study drugs (Vehicle Cream QD and Vehicle Cream BID), showing the same study visits shown here. Continue for other parameters.**  
 Sort alphabetically by parameter.

Abbreviations: BID = twice daily; QD = once daily; SD = standard deviation.  
 Note: Subjects are summarized by treatment received. Results from the thyroid panel are included. Baseline is the last non-missing measurement taken before the first application of study drug. Change from baseline is calculated as result – baseline result.  
 Reference Listings: 16.2.8.1.1, 16.2.8.1.4

Table 14.3.5.1.2.1  

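### Laboratory tables rest on scheduled values in Low/Normal/High categories, so between-visit abnormal values and confirmatory repeats are only listed, ungraded, and no laboratory table counts subjects per arm at Grade 3 or higher

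*SAP*

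**What the plan says.** SAP 9.3 plans descriptive summaries of observed values and changes by visit, frequencies for categorical urinalysis results, and a shift table of "The number of subjects with clinical laboratory values below, within, or above the normal range by study visit and in relation to baseline". The tables listed in SAP 13.1.3.5 are all of these kinds, for example "Cohort 2: Shift from Baseline in Hematology Laboratory Results (Standard Units) by Study Visit". The preceding entry, "13.1.3.4. Abnormal Laboratory Values", is filled in as NA.

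For repeat samples, SAP 6.1.5.1 says: "Unscheduled, early termination, and/or repeated measurements will only be included if a scheduled measurement is not available". The value must also fall inside an analysis window. Other repeats are listed.

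The protocol gives such samples a role. Section 5.6: "Unscheduled visits may be necessary to repeat testing following abnormal laboratory results". Section 4.10 discontinues treatment for "A treatment-emergent severe (Grade 3 or higher) laboratory abnormality (confirmed by repeat sample" (closing bracket omitted).

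**The concern.** The protocol defines a laboratory threshold serious enough to stop dosing, in terms of a CTCAE-type grade and a repeat sample. The planned laboratory tables use neither. They have no grade categories, and the repeat sample is excluded whenever the scheduled one exists.

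This is the first study of the cream in humans (protocol 2.3), and change in laboratory parameters is a stated safety endpoint in both cohorts (SAP 2.2.2). A reader of the report will want to know how many subjects in each arm reached Grade 3 or higher, and a reported zero would be useful too. As planned, that number has to be worked out by grading listed values by hand, or inferred from AE tables that depend on the finding having been recorded as an AE.

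**Working it through.** The plan gives no figure to reproduce, so this is mainly a reading of its parts against each other.

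**1. Table types.** SAP 13.1.3.5 lists 14 laboratory tables: 8 by-visit summaries (6 quantitative, 2 qualitative urinalysis) and 6 shift tables. None is graded, none gives a worst post-baseline value, and none counts confirmed abnormalities. The chemistry shift shell for Cohort 1 (Table 14.3.5.1.2.1) heads its axes with the word Grade, but the categories are Missing, Low, Normal and High. A value just above range and a Grade 4 value fall in the same cell.

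**2. The repeat rule against the Cohort 2 windows (SAP Table 4).** The chemistry summary shell shows Baseline and Weeks 4, 8 and 12, and says "Repeat this page for the remaining study drugs (Vehicle Cream QD and Vehicle Cream BID), showing the same study visits shown here".

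- Days 23-42, 43-70 and 71-90 (Weeks 4, 8, 12): each has a scheduled draw, which takes precedence.
- Days 2-22 (Week 2) and Day 91 onward (Week 13): no scheduled laboratory draw. SAP 6.1.5.1 and Table 4 would admit an unscheduled value here, but the shells have no row for it. The SAP does not resolve this.

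**3. Example (assumed days).** A scheduled Day 29 value is normal, an unscheduled Day 36 value is Grade 3, and a Day 38 repeat confirms it. All three lie in Days 23-42. The Week 4 shift shows Normal, and the Day 36 and Day 38 values are listed only. If instead the Day 29 scheduled value is itself Grade 3, the shift table shows it as out of range and it enters the minimum or maximum. Only its grade and its confirmation are lost.

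**4. Listings.** Listing 16.2.8.1.1 carries a reference-range flag and a clinical-significance interpretation, but no CTCAE grade.

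**5. Likely size.** Inputs are the oral rheumatoid arthritis study (protocol 2.3.2 and Table 1) and the exposure ceiling (protocol 2.4.1).

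- At 0.5, 1 and 2 mg: 25 + 24 + 23 = 72 subjects, with 0 Grade 3 laboratory cases listed. Two-sided 95% Clopper-Pearson upper limit = 1 - 0.025^(1/72) = 4.99%.
- Applied to the arms: 61 x 0.0499 = 3.05 and 31 x 0.0499 = 1.55. These are upper limits, not expectations.
- At 4 mg: 2/40 = 5.0% (95% CI 0.6% to 16.9%). At 8 mg: 2/45 = 4.4% (0.5% to 15.1%).
- At 100% absorption the 0.3% cream gives 1.5 mg/day QD, and by doubling 2 x 1.5 = 3.0 mg/day BID. The BID arm stays at or below 2 mg/day if absorption is at most 2/3.0 = 67%. The protocol expects a small fraction.

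**The case against.** The strongest reply is that these cases already have a route into graded, per-arm tables. Protocol 4.8 treats the 4.10 stops as adverse events, 5.7.1 allows an abnormal laboratory finding to be an AE, and 5.7.5 grades AEs on CTCAE 5.0. SAP Table 14.3.1.3 then gives AEs by preferred term and maximum grade, Table 14.3.1.5 gives those leading to drug discontinuation, and the listing in Table 14.3.3.1 shows the grade of each. AEs are also collected at unscheduled visits (protocol 5.6). Protocol 6.3.4 asks for descriptive summaries and out-of-range shifts, and the SAP supplies them.

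Most of this stands. What remains is narrow. No text requires every Grade 3 value to be recorded as an AE. The severity table splits by preferred term, so it gives no per-arm total of subjects at the laboratory threshold. The discontinuation table shows neither grade nor confirmation.

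A reader might infer three stronger things that the documents do not support:

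- *That the tables leave out the values that matter most for safety.* An abnormal scheduled draw, which is one ordinary trigger for a repeat, stays in the shift table and in the minimum and maximum.
- *That no repeat or unscheduled value can ever enter a laboratory table.* One can if the scheduled draw was missed, and for Days 2-22 and Day 91 onward the SAP text and its shells point in different directions.
- *That the SAP breaches the protocol.* It meets section 6.3.4.

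**Conclusion.** The point holds as a modest gap in reporting. When a scheduled value exists, abnormal values found between visits and confirmatory repeats reach only ungraded listings. No laboratory table gives a per-arm count at Grade 3 or higher, or at the confirmed threshold in protocol 4.10. The sponsor should close the gap, but it is neither an error nor a breach, and no efficacy conclusion is touched. Stopping decisions for individual subjects do not depend on these tables.

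The numbers involved are likely to be small. The size estimate assumes that each listed oral case is one subject, that the list of Grade 3 events is complete (the protocol says only that they included these cases), that it covers the groups as randomized (its period is not stated), and that oral dose is a fair guide to systemic exposure from the cream.

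**What to change.** In SAP 9.3 and 13.1.3.4:

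- For Cohort 2, add by arm a shift from baseline grade to worst post-baseline CTCAE 5.0 grade, for those analytes in protocol Table 3 that have CTCAE 5.0 grading criteria. Name them in the SAP. Use every post-baseline value, including unscheduled and repeat samples. For the roughly 6 subjects in Cohort 1 a listing is enough.
- Keep the Low/Normal/High shifts, including for the thyroid tests, and extend them to the worst post-baseline value.
- Add a per-arm count of subjects with a treatment-emergent Grade 3 or higher value. Add a sub-count confirmed by a repeat or unscheduled sample drawn to check that value before the next scheduled draw. Taking whatever sample comes next would not match protocol 4.10, because it could be a routine draw four weeks later.

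The cost is modest programming on data already collected, plus a written rule linking a Grade 3 value to its check sample. The downside is that the tables may be nearly empty. No new data are needed and no efficacy analysis changes.

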#### **9.4. Vital Signs**

Descriptive summaries of observed values and changes from baseline will be calculated for systolic blood pressure, diastolic blood pressure, heart rate, height, weight, BMI, and oral body temperature by treatment group within cohort and study visit.

#### **9.5. 12-Lead Electrocardiograms**

Descriptive summaries for observed values and change from baseline will be presented for 12-lead electrocardiogram (ECG) measures of PR interval, QRS interval, QT interval, QTc interval (Fridericia's [QTcF] correction method), and heart rate. These summaries will be presented by study visit and treatment group within cohort.

The number and percentage of subjects with each ECG investigator interpretation (normal; abnormal, not clinically significant; or abnormal, clinically significant) will be displayed for each treatment group within cohort and study visit.

#### **9.6. Physical Examination**

The number and percentage of subjects with normal and abnormal findings in the physical examination will be displayed at each study visit and treatment group within cohort.

#### **9.7. Concomitant Medications**

Prior and concomitant medications will be summarized descriptively by treatment within cohort, Anatomical Therapeutic Chemical (ATC) Class Level 4, and Preferred Term using counts and percentages.

Prior medications will be presented separately from concomitant medications. Medications that started before the first application of IP will be considered prior medications whether or not they were stopped before the first application of study drug. Any medications continuing or starting after the first application of study drug will be considered to be concomitant. If a medication starts before the first application of study drug and continues after the first application of study drug it will be considered both prior and concomitant.

#### **9.8. Modified Total Lesion Symptom Score (mTLSS)**

The modified Total Lesion Symptom Score (mTLSS) is used to determine the intensity of features as part of the IGA Severity Score. The total mTLSS is calculated as the sum of scores (0 = absent, 1 = mild, 2 = moderate, 3 = severe) assigned by the investigator for the chronic hand eczema parameters.

This endpoint was removed from the protocol as of amendment 1 (11May2020), thus a limited number of subjects and visits had data collected. The mTLSS results will be listed only.

## 10. CHANGES FROM PLANNED ANALYSIS

The following analysis populations have been added:

- The PRU4 population has been added to facilitate WI-NRS analysis on the ITT population;
- The PNR4, PNR3, and PNR2 populations have been added to facilitate Pain NRS analysis for subjects achieving a 4-point, 3-point, and 2-point reduction from baseline, respectively; and
- The All Treatment population has been added to facilitate Cohort 1 efficacy analyses.
- The ND population has been added to facilitate Cohort 2 analyses of nail dystrophy.

These populations are not included in the protocol.

The exploratory endpoint is change from baseline in nail dystrophy; since no baseline measurement will be collected for millimeters of normal nail distal to cuticle, it will be assumed that the amount of normal nail at baseline is 0 mm.

The definition of compliance was updated to exclude subjects who missed more than 3 consecutive days of dosing, versus subjects who missed more than 3 consecutive doses.

The following secondary endpoints were added upon request by the Sponsor:

- The rate of achievement of IGA of “clear” or “almost clear” PLUS at least a 2-point improvement from Baseline at Week 13
- The rate of achievement of at least a 2-point improvement from baseline at Week 13
- The rate of achievement of IGA of “clear” or “almost clear” at Week 13
- Change in IGA score at Week 13 as compared to baseline
- Change in WI-NRS pruritus score at 1, 3, 5, 6, 7, 9, 10, 11, and 13 compared to baseline (Weeks 2, 4, 8, and 12 were already included)
- Percent change in WI-NRS pruritus score at 1, 2, 3, 4, 5, 6, 7, 8, 9, 10, 11, 12, and 13 weeks after first application of study drug compared to baseline
- Change and percent change in HECSI score at Weeks 2, 4, 8, 12, and 13 compared to baseline
- Achievement of HECSI-75
- Percent change in Pain NRS score from Baseline to at 1, 2, 3, 4, 5, 6, 7, 8, 9, 10, 11, 12, and 13 weeks after first application of study drug
- The rate of achievement of  $\geq 3$ -point reduction from baseline in Pain NRS score at 1, 2, 3, 4, 5, 6, 7, 8, 9, 10, 11, 12, and 13 weeks after first application of study drug in subjects with baseline Pain NRS score of at least 3
- The rate of achievement of  $\geq 2$ -point reduction from baseline in Pain NRS score 1, 2, 3, 4, 5, 6, 7, 8, 9, 10, 11, 12, and 13 weeks after first application of study drug weeks in subjects with baseline Pain NRS score of at least 2

- Percent change from baseline in QOLHEQ score at each visit

The following treatment comparisons were added:

- ARQ-252 cream (all strengths and dose frequencies) versus vehicle cream (all dose frequencies)
- ARQ-252 cream 0.3% (all dose frequencies) versus vehicle cream (all dose frequencies)

For all efficacy treatment comparisons, vehicle cream will be pooled for analysis over both dose frequencies.

Efficacy analysis for Cohort 1 was not specified in the protocol, however, upon request from Sponsor, all efficacy data collected for Cohort 1 (IGA, HECSI, average weekly WI-NRS, average weekly Pain NRS, and % BSA affected by disease) will be summarized.

Subgroup analyses for IGA Success by study site (Week 12 only) and by baseline IGA severity were added.

An analysis of HECSI-75 and total % BSA affected by disease were also requested to be added.

All analyses of time to event (i.e., time to IGA of “clear” or “almost clear”; time to the first achievement of  $\geq 4$ -point reduction from Baseline in WI-NRS pruritus score in subjects with Baseline WI-NRS pruritus score of at least 4; and time to the first achievement of  $\geq 4$ -point reduction from Baseline in Pain NRS score in subjects with Baseline Pain NRS score of at least 4) were removed at the request of the sponsor.

